5.4 Analysis Plan for Secondary Objectives

In addition to HAQ DI score, the effect of adalimumab will also be assessed by the secondary outcome measures which are changes to the Short Form 36-Item Health Survey (SF-36) domain scores, EuroQol 5 dimension 3 level (EQ-5D-3L) index, WPAI outcomes, and Patient Treatment Satisfaction Questions at 12 and 24 weeks after the initiation of adalimumab in RA.

- As to the Short Form 36-Item Health Survey (SF-36) domain scores, the Excel Table 4 summarizes the changes in PCS T-score and MCS T-score at 12 and 24 weeks after the initiation of adalimumab; these changes will be summarized as the mean, SD, minimum, maximum, median, 95% confidence interval; and the mean change will be tested with paired t-tests with p-value listed in the table.
- As to the EuroQol 5 dimension 3 level quality of life questionnaire, the Excel Table 5 summarizes the changes in EQ-5D-3L index at 12 and 24 weeks after the initiation of adalimumab; these changes will be summarized as the mean, SD, minimum, maximum, median, 95% confidence interval; and the mean change will be tested with paired t-tests with p-value listed in the table.
- As to the WPAI outcomes, the Excel Table 6 summarizes the changes in percent overall work impairment and percent activity impairment at 12 and 24 weeks after the initiation of adalimumab; these changes will be summarized as the mean,

SD, minimum, maximum, median, 95% confidence interval; and the mean change will be tested with paired t-tests with p-value listed in the table.

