The SF-36 is a patient-reported questionnaire of patient health-related QoL. It measures generic health concepts relevant across age, disease, and treatment groups. There are 36 items in total and the recall period is the last 4 weeks. The SF-36 consists of eight scaled scores, which are the weighted sums of the questions in their section. Each scale is directly transformed into a 0-100 scale. Completion time for the SF-36 is approximately 10 minutes. The full version of SF-36 is presented in Appendix E.

EuroQol 5 dimension, 3 level quality of life questionnaire (EQ-5D-3L)

The EQ-5D-3L measures the patient's overall health state in a descriptive system of health-related QoL states consisting of five dimensions (mobility, self-care, usual activities, pain/discomfort, and anxiety/depression) each of which can take one of three responses. The responses record three levels of severity ('no problems', 'some problems', and 'extreme problems') within a particular EQ-5D-3L dimension (14, 15). In addition, a VAS rates current health state between 0-100. The EQ-5D-3L results can be converted to health utility scores. Completion time for the EQ-5D-3L is approximately 2-3 minutes. The full version of EQ-5D-3L is presented in Appendix F.

Work Productivity and Activity Impairment (WPAI)

The WPAI is a patient-reported questionnaire to measure work and activity impairment during the past seven days. It determines employment status, hours missed from work due to the disease (i.e. RA), hours missed from work for other reasons, hours actually worked, the degree to which the disease affected work productivity while at work and the degree to which the disease affected activities outside of work. Additional questions around employment status will be incorporated into the survey. The completion time for the WPAI is approximately 2-5 minutes. The full version of WPAI is presented in Appendix G.

All of the above questionnaires will use the validated Chinese version.

Patient Global Impression of Change (PGIC)

The PGIC measures the patient's perceptions of changes in their disease. It consists of one question asking about the change in their condition; for this study, the base will be "since you initiated your adalimumab treatment". The completion time for the PGIC is less than 1 minute. The full version of PGIC is presented in Appendix H.

Patient Treatment Satisfaction Questions

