approximately 70 days after the Week 24 dosing or the last dose of adalimumab to determine the status of any ongoing AEs/SAEs or the occurrence of any new AEs/SAEs. The information will be recorded on the appropriate in eCRF page.

For subjects that are considered lost to follow-up, reasonable attempts must be made to obtain information on the final status of the subject. At a minimum, two phone calls must be made and one certified letter must be sent.

9.3 **Variables**

Variables (as observed):

Primary Variable

- Change in HAQ DI score at week 24 from baseline

Secondary Variable

- Change in other PROs (SF-36 domain scales, EQ-5D Index, Work Productivity and Activity Impairment Questionnaire [WPAI]) from baseline to weeks 12 and 24
- Change in HAQ DI score at week 12 from baseline
- Number and percent of patients achieving a clinically meaningful improvement on the HAQ DI, from baseline to weeks 12 and 24
- Healthcare Resource Utilization (HCRU) at baseline, 12 and 24 weeks

Exploratory Variable

- Difference of the change in HAQ DI score from baseline to 24 weeks between as observed population and withdrawal population
- Change in patient satisfaction questions from baseline to weeks 12 and 24
- Patient's impression of change at weeks 12 and 24 from baseline
- Association between disease severity and PROs
- Association between change in disease severity and change in PROs

9.4 **Data Sources**

Case Report Forms (CRFs) and patient questionnaires.

Collection of data includes but not limited to subject demographics, clinical history, comorbidities, spontaneous adverse events, and concomitant medications. The following questionnaires will be utilized to collect data directly from participating subjects:

- EQ-5D
- SF-36
- HAQ DI
- WPAI

- HCRU
- Patient Global Impression of Change (PGIC)
- Patient Treatment Satisfaction Questions

9.5 **Study Size**

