9.7.5 Secondary Endpoint Analysis

The main secondary endpoint variable will be the change in HAQ DI at 12 weeks after the initiation of adalimumab.

The objective of endpoint analysis will be to demonstrate that treatment with adalimumab improves functioning as measured by HAQ DI in subjects with RA compared to baseline.

The main secondary analysis will be summarized as the mean and 95% confidence interval and will be tested with a paired t-test without adjusting for baseline disease severity. For sensitivity analysis, the mean change in HAQ DI at Week 12 will be analyzed using ANOVA adjusting for baseline disease severity.

Other secondary analyses include:

- Change in other patient reported outcomes (SF-36 domain scales, EQ-5D Index, WPAI total lost productivity) at weeks 12 and 24 after the initiation of adalimumab, in those patients continuing on adalimumab (as observed population). These changes will be summarized as the means and 95% confidence intervals and will be tested with paired t-tests.
- Number and percent of patients achieving a clinically meaningful improvement on the HAQ DI, as defined by a -0.22 point improvement or greater, at weeks 12 and 24 after the initiation of adalimumab, in those patients continuing on adalimumab (as observed population).

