2.2 Secondary Objectives

- To describe the change in HAQ DI score at 12 weeks after the initiation of adalimumab, in those patients continuing on adalimumab (as observed population). This change will be summarized as the mean and 95% confidence interval and will be tested with a paired t-test without adjusting for baseline disease severity. For sensitivity analysis, the mean change in HAQ DI at Week 12 will be analyzed using ANOVA adjusting for baseline disease severity.
- To describe the change in other patient reported outcomes (SF-36 domain scales, EQ-5D-3L index, WPAI total lost productivity) at weeks 12 and 24 after the initiation of adalimumab, in those patients continuing on adalimumab (as observed population). These changes will be summarized as the means and 95% confidence intervals and will be tested with paired t-tests.
- To summarize the number and percent of patients achieving a clinically meaningful improvement on the HAQ DI, as defined by a -0.22 point improvement or greater, at weeks 12 and 24 after the initiation of adalimumab, in those patients continuing on adalimumab (as observed population).

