$$\text{z-score} = \frac{([\text{0-100 score}] - [83.29094])}{(23.75883)}$$

Z-scores are then transformed into T-scores (mean = 50, SD = 10) using the following formula:

$$T\text{-Score} = 50 + (z\text{-score} \times 10)$$

Step 6: Scoring the physical and mental component summary measures using health domain z scores

The Physical Component Summary (PCS) and Mental Component Summary (MCS) measures are then scored using a three-step procedure, regardless of whether a standard or acute form was administered. First, the eight health domain scales are standardized using means and standard deviations from the 2009 U.S. general population. Second, these standardized scores are aggregated using weights (factor score coefficients) from the 1990 US general population. Computation of an aggregate physical component score consists of multiplying each health domain scale z-score by its respective physical factor score coefficient and then summing the eight products. Similarly, an aggregate mental component score is obtained by multiplying each health domain scale z-score by its respective mental factor score coefficient and summing the eight products. To illustrate, a portion of the formula for aggregating scales when estimating a standard form of aggregate mental component score is as follows:

$$\begin{aligned} \text{Aggregate mental component score} = \\ (\text{PF z-score} \times -0.22999) \dots + (\text{MH z-score} \times 0.48581) \end{aligned}$$

Third, aggregate PCS and MCS scores are standardized using a linear T-score transformation with a mean of 50 and a standard deviation of 10. The formulas for computing the norm-based T score for each component summary measure are:

$$\begin{aligned} \text{PCS T-score} &= 50 + (\text{Aggregate physical component score} \times 10) \\ \text{MCS T-score} &= 50 + (\text{Aggregate mental component score} \times 10) \end{aligned}$$

Step 7: Scoring the response consistency index (RCI)

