5.5 Analysis Plan for Exploratory Objectives

- Excel Table 7 describes the change in 4 patient satisfaction questions at weeks 12 and 24 after the initiation of adalimumab, in those patients continuing on adalimumab (observed population). These changes will be summarized as number and percentage of each response and compared with Wilcoxon signed rank test shown by p-value1. Satisfaction will also be dichotomized and analyzed over time with Cochran-Armitage test for trends shown by p-value2 in the table.
- Excel Table 8 summarizes the patients' global impression of change in RA at weeks 12 and 24 after the initiation of adalimumab, in those patients continuing on adalimumab (as observed population). Each response (very much better, much better, a little better, no change, a little worse, much worse, and very much worse) will be summarized as number and percentage.
- Descriptive statistics will be presented for post-index overall RA related direct healthcare resource utilization (Excel Table 9)
 - Consultations/visits to healthcare professionals for treatment of RA (number of patients with ≥ 1 visit; categorized by the treatment department listed in 3.5.4)
 - Procedures received when visiting the healthcare professional(s) for treatment of RA (number of patients with ≥ 1 procedure; categories listed in 3.5.4)
 - surgeries received when visiting the healthcare professional(s) for treatment of RA (number of patients with ≥ 1 surgery; categories listed in 3.5.4)
 - Hospitalizations in relation to RA (number of patients with ≥ 1 admission)
 - Length of stay in days (mean, SD, median)
 - Concomitant medications taken for RA (number of patients with ≥ 1 medication; categories listed in 3.5.4))
- Associations between disease severity (measured by DAS28) and PROs (HAQ DI score, SF-36 domain scales, EQ-5D-3L index, WPAI outcomes) will be analyzed using the bivariate linear regression model (Excel Table 10.1). Separate models will be estimated to identify the association between DAS28 and each of the PROs.
- Additionally, in Excel Table 10.2, separate bivariate liner regression models will be estimated to identify the association between change in DAS28 and change in each of the PROs at 12 and 24 weeks after baseline respectively.

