6. LIST OF TABLES AND FIGURES IN EXCEL WORKBOOK

Results of the analysis for this study as outlined above will be summarized using MS Excel tables and will be presented as follows:

Excel Tables / Figures	Description
1	Demographic Characteristics at Baseline
2	Clinical Characteristics at Baseline
3.1	Change in HAQ DI at Weeks 12 and 24 after Initiation of Adalimumab
3.2	Change in HAQ DI at Weeks 24 after Initiation of Adalimumab - Observed VS Withdrawal Population
4	Change in SF-36 Domain Scales at Weeks 12 and 24 after Initiation of Adalimumab
5	Change in EQ-5D-3L Index at Weeks 12 and 24 after Initiation of Adalimumab
6	Change in WPAI at Weeks 12 and 24 after Initiation of Adalimumab
7	Change in Patient Satisfaction Questions at Weeks 12 and 24 after Initiation of Adalimumab
8	Patients' Global Impression of Change at Weeks 12 and 24 after Initiation of Adalimumab
9	Post-index Healthcare Resource Utilization - RA Related
10.1	Associations between Disease Severity and PROs
10.2	Associations between Change in Disease Severity and Change in PROs
11	GLM - Modifying Effects on Changes in PROs

Please see the document, "AbbVie_ROCKI_Tableshell_V0.2_15Jan2018_Taiwan.xlsx" for the full set of table shells.

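### SAP 5.4 plans the SF-36 change analysis only for the two component summaries (PCS and MCS), although the declared secondary endpoint is the eight domain scales

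*SAP*

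**What the plan says.** **The declared endpoint.** Protocol 9.3 lists among the secondary variables "Change in other PROs (SF-36 domain scales, EQ-5D Index, Work Productivity and Activity Impairment Questionnaire [WPAI]) from baseline to weeks 12 and 24". Protocol 9.7.5 repeats it as a secondary analysis, "Change in other patient reported outcomes (SF-36 domain scales, EQ-5D Index, WPAI total lost productivity) at weeks 12 and 24", and asks for means, 95% confidence intervals and paired t-tests. Protocol 9.2.4.7 describes the SF-36 as eight scales and adds: "Each scale is directly transformed into a 0-100 scale". SAP 2.2 carries the same endpoint and the same method: "To describe the change in other patient reported outcomes (SF-36 domain scales, EQ-5D-3L index, WPAI total lost productivity) at weeks 12 and 24".

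**The planned analysis.** The opening sentence of SAP 5.4 also speaks of domain scores. Its SF-36 bullet, which says what will be tabulated and tested, reads: "domain scores, the Excel Table 4 summarizes the changes in PCS T-score and MCS T-score at 12 and 24 weeks". The descriptive statistics, confidence interval and paired t-test in that bullet attach to those two scores.

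**The table title.** SAP section 6 lists Table 4 as "Change in SF-36 Domain Scales at Weeks 12 and 24 after Initiation of Adalimumab".

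**Other uses of the domains.** SAP 5.5 has regressions in Table 10.1: "Associations between disease severity (measured by DAS28) and PROs (HAQ DI score, SF-36 domain scales, EQ-5D-3L index, WPAI outcomes". Table 10.2 does the same for change scores. Table 11 fits effect-modifier models to the primary and secondary outcomes, which SAP 2.3 identifies as the PROs.

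**The concern.** The SAP names one endpoint in its objectives and its list of tables, and specifies the analysis of another in the section an analyst would program from. Protocol 9.7.1 requires all analysis to follow the approved plan. An analyst who follows the 5.4 bullet to the letter would therefore leave the declared SF-36 endpoint without an estimate, interval or test. Two summary scores that the protocol never mentions would appear under a domain-scales title.

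This is more than loose terminology, because the SAP itself separates the two. In SAP 3.5.1, Steps 3 to 5 score the eight health domains, and Step 6 then builds PCS and MCS as weighted sums of the eight domain z-scores. Some of those weights are negative, so a summary can move against one of its own components. A table holding only PCS and MCS would not show which domains changed. The SAP text gives no reason for the switch and does not record it as a change from the protocol.

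**Working it through.** The documents state no sample size or power figure for the SF-36, so there is no figure of the plan's own to reproduce. The check is a comparison of texts, a count, and three short calculations that show size.

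**1. Texts side by side**

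| Place | SF-36 measure | Change summary and paired t-test |
|---|---|---|
| Protocol 9.3 | domain scales | variable declared |
| Protocol 9.7.5 | domain scales | yes |
| SAP 2.2 | domain scales | yes |
| SAP 5.4, opening sentence | domain scores | not specified there |
| SAP 5.4, SF-36 bullet | PCS and MCS T-scores | yes |
| SAP 6, Table 4 title | domain scales | title only |
| SAP 5.5, Tables 10.1 and 10.2 | domain scales | no, regressions on DAS28 |
| SAP 5.5, Table 11 | secondary outcomes (PROs) | no, effect-modifier models |

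The 5.4 bullet stands alone against the rest. The regressions in 5.5 ask how the scales relate to disease activity or to baseline factors. They do not give the mean within-patient change that the endpoint calls for.

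**2. Count of analyses**

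- Declared: 8 scales × 2 visits = 16.
- Planned in the 5.4 bullet: 2 scores × 2 visits = 4.
- Declared analyses covered by the bullet: 0 of 16.

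**3. Are PCS and MCS equivalent to the domains?** SAP 3.5.1 Step 6 prints two of the eight MCS weights, −0.22999 for Physical Functioning (PF) and +0.48581 for Mental Health (MH), and sets the MCS T-score to 50 + 10 × aggregate. The contribution to MCS of a gain of 1 population SD is:

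- PF alone: 10 × (−0.22999) = −2.30 T-points.
- MH alone: 10 × 0.48581 = +4.86 T-points.
- Both together, from these two terms: 10 × (0.48581 − 0.22999) = +2.56 T-points.

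Improved physical function therefore pulls MCS down and hides about half of an equal gain in mental health. The other six weights are not printed, so these figures illustrate the direction and are not predictions for the study.

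**4. Can the domain analyses be done?** Inputs: 100 patients less the protocol's 10% dropout gives n = 90; two-sided paired t-test; 80% power. The standardised mean change d solves power = 0.80 with noncentrality d√90.

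- At alpha 0.05: d = 0.299.
- At 0.05/16 = 0.003125, a strict Bonferroni level chosen here for illustration: d = 0.410.
- With the SAP's 13% dropout (n = 87), the first figure becomes 0.304.

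Sample size is no reason to drop the domains.

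**5. Price of more tests.** If no domain changes and each test is run at 0.05, the expected number of false positives is 16 × 0.05 = 0.8, against 4 × 0.05 = 0.2. If the tests were independent, the chance of at least one would be 1 − 0.95^16 = 0.56, against 1 − 0.95^4 = 0.19. SF-36 scales are correlated, so these last two are illustrations only.

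**The case against.** The best case for the plan is that the domain analysis is not lost. SAP 2.2 states it in full, with intervals and paired tests. The opening of 5.4 and the title of Table 4 both say domains, all eight domains are scored in 3.5.1, and the layout sits in a table-shell workbook that is not among the documents. Read as a whole, the SAP may intend domain rows with PCS and MCS added. That much stands: the defect is a contradiction within the SAP text, and whether the final table would lack domain rows cannot be established here. It does not remove the need for correction, because the one passage that specifies the table's content names only PCS and MCS.

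Several narrower points also have weight. The MCS figures use two of eight weights and a constructed case. The power figures answer a doubt about feasibility that the documents do not raise. Step 5 gives a stated reason for T-scores, comparability across domains, so the 0-100 metric is not the only defensible choice, although it is the one the protocol describes. The sponsor could instead declare PCS and MCS as a justified change from the protocol. None of this defends the text as it is written.

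Step 5 also prints one unlabelled mean and SD (83.29094 and 23.75883), although the sentence before it calls for each scale's own values. This is a labelling matter and carries no weight here. A constant divisor rescales every change by 10/23.75883 = 0.4209 and leaves a single domain's paired t-test unchanged.

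**Conclusion.** The concern holds. SAP 5.4 as written contradicts the endpoint declared in Protocol 9.3 and 9.7.5 and in SAP 2.2, and it contradicts the SAP's own title for Table 4. Taken literally, it replaces 16 declared domain analyses with 4 analyses of scores that the protocol does not name and that are not equivalent to the domains.

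The conclusion rests on the text alone and needs no numerical assumption. The one thing that cannot be seen is the table-shell workbook. If it has domain rows, the practical loss disappears but the wording still needs correcting. The matter concerns one secondary patient-reported outcome in a single-arm observational study. The primary analysis, sample size and safety evaluation are untouched. It should be corrected before the analysis is run.

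**What to change.** - **SAP 5.4.** Rewrite the SF-36 bullet so that Table 4 gives mean change, 95% confidence interval and paired t-test for each of the eight domain scales at weeks 12 and 24. Use the 0-100 scores from Step 4, the metric in Protocol 9.2.4.7. On that metric the endpoint depends on no population norm.
- **PCS and MCS.** Keep them in the table, labelled supplementary. If the sponsor prefers them as the endpoint, that should be declared and justified as a change from the protocol.
- **Consistency.** Make SAP 2.2, 5.4 and 6 and the table shells name the same measures and the same metric.
- **P-values.** Label the SF-36 p-values nominal.
- **Minor.** In Step 5, say which scale the printed mean and SD belong to, and tabulate the others or cite the scoring manual or software. If that pair were programmed for every scale, T-score levels and changes in PCS and MCS would be affected.

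The cost is a few sentences in the SAP and eight rows per visit in one table, from scores the SAP already derives. The drawback is more secondary tests (0.8 expected false positives against 0.2 if nothing changes), which is why the nominal label is needed.

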Approximately 100 patients diagnosed with RA will be recruited. The planned sample size provides at least 95% power for detecting a statistically significant improvement in HAQ-DI (Δ HAQ-DI < 0) assuming a mean Δ HAQ-DI of -0.21 and a standard deviation of 0.5 (reference 11), at two-sided significance level of 0.05 and accounting for a 10% dropout rate. The sample size also provides at least 95% power for detecting a statistically significant clinically meaningful improvement in HAQ-DI (Δ HAQ-DI < -0.22) assuming a mean Δ HAQ-DI of -0.5 and a standard deviation of 0.7, at two-sided significance level of 0.05 and accounting for a 10% dropout rate. For the secondary endpoint WPAI, the sample size provides 63% power for detecting a statistically significant improvement in “hours of work lost” at two-sided significance level of 0.05 and accounting for a 10% dropout rate, assuming a mean change in “hours of work lost” of 10 and standard deviation of 30 and assuming a 55% employment rate in the study population.

9.6 **Data Management and Storage Process**

9.6.1 **Data Management**

Data management and data quality check will be performed to remove errors and inconsistencies in order to assure the appropriateness of the study data set to assess the study objectives. Data entry screens will be developed and tested prior to initiating data collection to reduce data entry errors. If required, IMS will provide AbbVie with data for analysis.

Each site coordinator will be instructed to answer patients’ queries which may arise in relation to the questionnaires and check the patients’ input to make sure all questions are answered.

9.6.2 **Storage Process**

Following data quality checks, each dataset will be converted to SAS and merged for analysis. All information included in the CRF and the patients’ questionnaires will be checked in order to detect possible queries to solve and will be extracted to a specifically designed database, where it will be validated by IMS personnel to ensure its quality. Finally, data analysis will be conducted and final results reported.

The databases will be stored in IMS data servers. Data servers are submitted to daily backups in order to increase the security on all data managed in the collection process.

All paper based questionnaires will be stored in a secured, locked area for a period of seven (7) years, after which all data will be shred using an agency specialized in disposal of confidential documents.

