Visual analogue scale (VAS) is the second part of the questionnaire, asking to mark health status on the day of the interview on a 20 cm vertical scale with end points of 0 and 100. There are notes at the both ends of the scale that the bottom rate (0) corresponds to “the worst health you can imagine”, and the highest rate (100) corresponds to “the best health you can imagine”. The respondents have to draw a line from the box on the questionnaire to the scale indicates the health state of the interviewed day; while ambiguous values (e.g. the line crosses the VAS twice) should be treated as missing values, which are coded as “999”. Eventually, the EQ-5D-3L results can be converted into a single index value; many different terms are in use for these index values, such as preference weights, preference-based values, utilities, QALY weights, etc.

Work Productivity and Activity Impairment (WPAI)

WPAI outcomes are expressed as impairment percentages, with higher numbers indicating greater impairment and less productivity (i.e., worse outcomes) as follows:

Questions

Q1 = currently employed

Q2 = hours missed due to specified problem

Q3 = hours missed other reasons

Q4 = hours actually worked

Q5 = degree problem affected productivity while working

Q6 = degree problem affected regular activities

Scores

Multiply scores by 100 to express in percentages.

- Percent work time missed due to problem

$$Q2 / (Q2+Q4)$$

- Percent impairment while working due to problem

$$Q5 / 10$$

- Percent overall work impairment due to problem

$$Q2/(Q2+Q4)+[(1-Q2/(Q2+Q4) \times (Q5/10)]$$

- Percent activity impairment due to problem

$$Q6 / 10$$

Patient Treatment Satisfaction Questions

The patient treatment satisfaction questions were developed de novo for this study and are not considered “validated” questions. There are totally 4 questions asking about the patients’ satisfaction with the following 4 aspects respectively:

1. The way RA treatment improves the morning stiffness in and around the joints.
2. The way RA treatment improves the mobility.
3. The way RA treatment improves the ability to perform daily living requiring fine motor skills.
4. The overall RA treatment.

There are totally 5 responses for each of the question: very satisfied, somewhat satisfied, neither satisfied nor dissatisfied, somewhat dissatisfied, and very dissatisfied.

3.5.2 *Exposure/Independent Variables of Interest*

- **Patient demographics (if data available)**
 - Date of birth

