4. SAMPLE SIZE AND POWER

Approximately 100 patients diagnosed with RA will be recruited. The sample size was calculated by assuming an alpha of 0.05 and a power of 0.80 in a two-sided test, resulting in 52 subjects required to recognize a statistically significant improvement in HAQ DI (-0.21) (11). Given the importance of other secondary endpoints, an improvement of 9.9 ± 25 hours of work time lost requires 58 subjects, assuming an alpha of 0.05 and a power of 0.80 in a two-sided test (12). However, since it is expected that approximately half the study population may no longer be working due to their age, approximately twice this number (100 patients) will be required to achieve the required number of respondents. We have also assumed a drop-out rate of 13% (assuming between 10%-15%).

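### The work-endpoint power is stated for hours of work lost, but the analysis plan names no change result in hours

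*SAP*

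**What the plan says.** - **Protocol 9.5** (repeated in the abstract) first gives the HAQ-DI power, then turns to the WPAI: "the sample size provides 63% power for detecting a statistically significant improvement in “hours of work lost” at two-sided significance level of 0.05". The inputs follow: "assuming a mean change in “hours of work lost” of 10 and standard deviation of 30", with 55% of patients employed and 10% dropout.
- **SAP 4** says that an improvement of 9.9 with SD 25 "hours of work time lost requires 58 subjects". It then roughly doubles that number to 100, because about half the patients may not be working. HAQ-DI needs only 52 there, so in the SAP it is the hours measure that leads to 100.
- **Protocol 9.7.5 and SAP 2.2** list "WPAI total lost productivity" as the WPAI variable to be analysed. Neither document defines that label.
- **SAP 3.5.1** defines four WPAI scores, all percentages. One of them is "Percent work time missed due to problem". Hours missed because of RA (item Q2) appears only as a component of these scores.
- **SAP 5.4** sets out the change analysis with paired t-tests: "the Excel Table 6 summarizes the changes in percent overall work impairment and percent activity impairment at 12 and 24 weeks".

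**The concern.** A power statement is useful only if it belongs to an analysis that will be run. Here the work power and the SAP's recruitment number rest on hours lost, while the planned tests are on two percent scores. Overall work impairment adds a 0–10 self-rating of productivity at work, and activity impairment is answered by non-workers too. Neither is a measure of hours.

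Two things are at stake. A reader may attach 63% or 80% power to a result on a different scale. And the report may not show whether any gain came from less absence or from better performance while at work. Work productivity is part of the stated study objective, and the rationale names payers among the audience.

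**Working it through.** **Inputs**

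| Input | Protocol 9.5 | SAP 4 |
|---|---|---|
| Enrolled | about 100 | about 100 |
| Dropout | 10% | 13% |
| Employed | 55% | about half (taken as 50%) |
| Mean change, hours | 10 | 9.9 |
| SD, hours | 30 | 25 |
| Two-sided alpha | 0.05 | 0.05 |
| Power | 63% (result) | 80% (target) |

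**Step 1: reproduce the 63%.** Employed pairs: 100 × 0.90 × 0.55 = 49.5. Standardised change: 10/30 = 0.333. Noncentrality: 0.333 × √49.5 = 2.35. The paired t-test power from the noncentral t distribution is 63.3% (62.8% at 49 pairs, 63.7% at 50). The normal approximation gives 65.0%. The protocol's figure is right, for hours.

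**Step 2: the SAP's 58.** Standardised change: 9.9/25 = 0.396. Required n = ((1.96 + 0.8416)/0.396)² = 50.05. Dividing by 0.87 for dropout gives 57.5, so 58 appears to include dropout already. Twice 58 is 116, not 100. With 100 × 0.87 × 0.50 = 43.5 pairs, the power for hours is about 72%.

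**Step 3: does the power carry over to the percent scores?** It cannot be computed, because the documents give no mean change or SD for them. What can be given is a range. With 43 to 50 employed pairs, 80% power needs a standardised change of about 0.44 to 0.40. For assumed SDs of 20 to 35 percentage points, that is a change of about 8 (0.404 × 20) to 15 (0.437 × 35) points in overall work impairment. For activity impairment even the number of pairs differs: non-workers answer it, so 87 to 90 pairs would be available (100 × 0.87 and 100 × 0.90), and the standardised change needed is about 0.30.

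**Step 4: do the SDs fit a weekly recall?** Neither size section gives a time unit. Item Q2 asks about seven days. Assume that the hours are weekly and that at most M can be missed, with M = 40 or 60 (assumed; the form sets no limit).

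- If absence only improves, with mean improvement m, the largest possible SD is √(m(M − m)).
- If changes go both ways, the fewest patients change when a share a goes from M to 0 and a share b from 0 to M. Then a − b = m/M and a + b = (SD² + m²)/M².

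| Mean / SD | M | Largest SD, improvement only | a (fully improve) | b (fully worsen) |
|---|---|---|---|---|
| 10 / 30 | 40 | √(10 × 30) = 17.3 | 44% | 19% |
| 10 / 30 | 60 | √(10 × 50) = 22.4 | 22% | 6% |
| 9.9 / 25 | 40 | √(9.9 × 30.1) = 17.3 | 35% | 10% |
| 9.9 / 25 | 60 | √(9.9 × 50.1) = 22.3 | 18% | 2% |

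Example for 10/30 and M = 40: a − b = 10/40 = 0.25 and a + b = 1000/1600 = 0.625, so a = 0.4375 and b = 0.1875.

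**The case against.** The other side has several good points.

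- **The study does not rest on hours.** The primary HAQ-DI has stated power of at least 95%, which reproduces (97.6% with 90 patients, mean −0.21, SD 0.5), and it is analysed. This stands. In the protocol, the 63% is a figure reported for one secondary endpoint.
- **No prespecified analysis was dropped.** The protocol's analysis sections never list hours as a variable. This stands: the mismatch is between the size sections and the analysis sections.
- **Hours are not ignored.** Item Q2 enters percent overall work impairment, which is tested. True, but no result in hours comes out. In addition, the form in Protocol Appendix G tells a patient who worked zero hours to skip the productivity rating that the overall score uses, and SAP 3.5.1 writes no rule for that case.
- **Percent work time missed may be analysed elsewhere.** SAP 5.5 regresses unspecified WPAI outcomes, and changes in them, on DAS28 (Tables 10.1 and 10.2), and the table shells are in a separate workbook that is not available here. This stands, but a regression on DAS28 does not give a mean change from baseline.
- **The undefined label probably means percent overall work impairment.** Likely, though neither document says so. It is a naming gap rather than clear evidence of a third measure.
- **The SD argument depends on assumptions.** It does. At a 60-hour maximum the required shares fall by half or more.

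**Conclusion.** The point holds for the work endpoint only. The stated work power belongs to change in hours lost, and SAP 5.4 plans no such result. The 63% is correctly calculated for hours on the protocol's inputs and says nothing about the two percent scores.

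A reader might infer that the study lacks a powered analysis, or that a promised hours analysis was removed. The documents support neither reading. A reader might also infer that the planning SDs are impossible. That goes too far as well: the time unit is not given, and the SAP cites an outside adalimumab study for its inputs that was not available here. The supportable statement is conditional. If the inputs are hours over seven days, with a maximum of 40 to 60 hours, both SDs exceed what improvement alone allows (about 17 to 22). An SD of 30 would then need about 44% fully improving and 19% fully worsening at 40 hours, or about 22% and 6% at 60 hours.

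**What to change.** 1. **SAP 5.4 / Table 6:** add change in hours missed due to RA (item Q2) and change in percent work time missed, which SAP 3.5.1 already defines. Give mean, SD and 95% CI at weeks 12 and 24 in patients employed at both baseline and that visit. Apply one paired test, on hours, as the measure for which power is stated.
2. **Protocol 9.7.5 and SAP 2.2:** replace the undefined label with percent overall work impairment, if that is the score meant.
3. **Protocol 9.5 and SAP 4:** state that the work power refers to hours lost under the assumed mean and SD, give the time unit of those inputs, and say that it does not apply to the percent scores. The text should not present 10/30 as established for weekly Q2 hours. The alternative is to restate power for percent overall work impairment with a justified mean and SD.

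The cost is two more table rows from data already collected, one more secondary test per visit, some wording changes, and a less favourable power statement.
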